Rationale for the study design: Pilot work with HOPE has determined that HOPE is associated with improved outcomes relative to standard shelter services alone. Given that there is no other existing PTSD treatment appropriate for this population that could serve as a comparison condition the next logical stage in evaluating the efficacy of HOPE is to determine if HOPE offers improvement over a credible control condition that controls for the nonspecific components of therapy. PCT (see appendix) is a problem-focused, supportive therapy that is frequently used as an attention-matched control condition in clinical trials of PTSD^{46, 47}. PCT does not incorporate any of the hypothesized active ingredients of HOPE (e.g., cognitive-restructuring, acquisition of new behavioral skills, safety planning, access to resources, and empowerment strategies), but does provide psychoeducation on PTSD. Further, PCT is also clinically realistic, as many practitioners incorporate this approach into their standard practice⁴⁸. Therefore, we chose to compare HOPE to PCT, in order to determine if components specific to HOPE are responsible for observed effects, rather than nonspecific factors consistent with supportive therapy. [name] who has established expertise in PCT⁴⁶ will assist in adapting PCT to meet the needs of the proposed study, as well as in the training and supervision procedures for the PCT arm of this study.

Sample and recruitment: Participants will be 186 women recruited over 27 months from six battered women's shelters in five different counties within a 55 mile radius of the University of Akron (see letters of support) and randomized either to receive HOPE ($n = 93$) or PCT ($n = 93$). Both treatments will start while women are residents of shelter and extend after they leave shelter. Given that the length of shelter stay is variable and outside of experimenter control, session frequency will be individualized based on length of shelter stay. We are currently employing this model in our work with HOPE with success (see C1). Participants in both treatment conditions will receive up to ten individual sessions while in shelter, and 16 sessions in for up

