Randomization: In order to ensure that the treatment conditions are balanced on variables that might influence outcome (i.e., use of psychotropic medications and substance use), participants in each subgroup will be assigned to their treatment condition using an urn randomization procedure⁵⁴. Urn randomization is a stratified randomization technique that randomly assigns participants in a given subgroup to treatment conditions, but systematically biases the randomization in favor of balance among treatment conditions. We will stratify participants according to comorbid substance use disorder (SUD) and use of psychotropic medications to obtain an equal distribution of participants using medications or with SUD in each condition.

Potential for Cross-Contamination: The shelter is a close community and participants in HOPE may share HOPE specific components with participants in PCT. We considered randomizing treatment assignment to shelter rather than participants in an effort to eliminate the potential for cross-contamination. However, this strategy significantly reduced our power and required a sample size that was not feasible or cost effective. Further, in our pilot work with HOPE only 2 participants in the control group reported that participants in HOPE shared HOPE-specific information with them, with exploratory analyses revealing no differences in PTSD outcomes between those who reported exposure and those who did not. Further, HOPE focuses on empowerment and provides individualized feedback and customized handouts, thus the content of HOPE cannot be easily learned through exposure to a handout or a brief conversation. However, to minimize the likelihood of cross-contamination between treatment and control groups, we will (1) instruct participants to not share their materials (i.e., workbook) with other shelter residents, (2) assess whether participants randomized to HOPE shared HOPE specific information with other shelter residents, and whether participants randomized to PCT were exposed to specific HOPE components during our follow-up procedures, and (3) assess use of HOPE specific skills in the PCT group in order to determine if women in PCT were actually implementing skills taught only in HOPE. Thus, we will try to minimize the potential for sharing HOPE-specific information and skills between participants, but also assess whether cross-contamination is a significant problem (see C3).

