Noncompleters: In general, women who do not attend at least 8 sessions (i.e., $\frac{1}{2}$ of sessions, as prior work with HOPE finds treatment effects when participants attend approximately 50% of sessions) will be considered noncompleters. Women will not be discontinued from the treatment protocol for noncompliance. All women will be invited to continue treatment and follow-up assessments. Given the unpredictable and demanding lives of our target group, most of whom are low-income, flexibility is important to make the treatment accessible to them (see assessment and retention sections for how we will address barriers in scheduling appointments).

Clinical Deterioration/Suicidal Risk. To increase safety, participants will be removed from the treatment phase of the trial as a result of clinical deterioration or suicidal risk (see E1 for procedures, assessment & definitions). Participants will remain in the research sample, be followed, and included in all analyses.

Therapists: Therapists for the intervention will consist of 4 community therapists who have been rated as qualified practitioners of HOPE or PCT (see below). Licensed, Master level (psychology, social work, counseling, or other related field) therapists will be recruited from the two local community mental health agencies who have served as our primary referral sources for this population throughout our pilot work (and thus are representative of the types of agencies most likely to treat victims of IPV who seek shelter). Each therapist will be required to have a minimum of two years of experience working with trauma populations, as well as training and experience in CBT interventions. Potential therapists will be interviewed by the PI. The interview will include questions about their training in trauma and CBT. Role-plays will also be used to assess the adequacy of their training and their ability to learn the proposed treatment protocols.

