Therapist training procedures: Procedures for training and monitoring therapists will mirror those used in prior research utilizing community therapists⁵⁵. [name], will assist in refining the training and monitoring protocols of community level therapists. To optimize the rapid acquisition and maintenance of therapist skills, supervision will initially be intensive, with supervision being titrated to skill level so that it becomes less intensive as therapists acquire more experience. [name] will oversee weekly group supervision sessions with all community therapists. [name] will provide individual supervision titrated to skill level to each of the community therapists. [name] and the project coordinator will review therapists' audiotapes on a weekly basis and provide feedback during individual and group supervision sessions. The therapists will be closely monitored for competence and adherence throughout the study and if at any time a therapist does not achieve good adherence, the therapist will be replaced with another therapist who will have received the training and completed the certification process. If a therapist has problems delivering the treatment, then data associated

with this therapist will not be included in any analyses. We are confident that we will be able to successfully train community therapists in HOPE, as we have successfully trained master-level graduate students in HOPE in our prior research. Further, we are using rigorous training procedures that have been successful in prior clinical trials with PTSD treatments⁵⁵. Finally, HOPE is a very structured treatment with a detailed and well scripted manual, leaving very little room for therapists to veer from standardized treatment procedures.

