The four community therapists will be trained in either the conduct of HOPE or PCT. We chose to train therapists in only one treatment modality in order to eliminate the risk of contamination in the control group and assure that HOPE is compared to a true attention-matched control condition. Therapists will be randomly assigned to deliver either HOPE or PCT. Existing systematic training programs (certification processes) in the conduct of HOPE and PCT that have been implemented in prior research will be used for the proposed study. As in prior research utilizing community therapists⁵⁵ each therapist will have two closely supervised training cases prior to taking on participants enrolled in the randomized trial. For both HOPE and PCT, the overall training objectives are for therapists to understand and learn to perform the intervention, to avoid using techniques or materials not part of the intervention, to ensure the use of relatively consistent procedures across different participants, and to deliver the intervention in a culturally sensitive manner. HOPE training (see training manual in appendix) includes a two-day workshop on HOPE conducted by [name], that includes lectures on IPV and PTSD, the theoretical conceptualization of HOPE, and the structure of, techniques used in, and conduct of HOPE sessions. The training program will also teach strategies for maintaining the therapist and participant safety when conducting HOPE sessions post-shelter, as well as procedures for managing emergency situations. Role-plays of appropriate and effective as well as faulty strategies to conduct the sessions, and strategies to manage participants whom may have difficulty in comprehending or utilizing the techniques will be included in the workshop. PCT training will also include a two-day workshop on PCT conducted by [name]. Drs. [name] and [name] will work closely with [name] in adapting the existing didactic training program for this study. Therapists will be trained in general issues in working with IPV victims, including strategies for managing emergencies. The workshop will include a description of the theoretical rationale behind PCT, as well as specific PCT strategies. Training will also be provided outlining specific strategies that are not to be used as a part of PCT (e.g., cognitive-restructuring, skills training, and other overlapping components with HOPE). Role-plays of appropriate and effective as well as faulty strategies to conduct the sessions, and strategies to manage more difficult clients will be included in the workshop.

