Prior to conducting analyses for the main project aims, a series of routine procedures will be conducted to ensure the data accuracy/adequacy. We will also examine the distribution of our key variables for skewness, variability, missing data, and outliers. Data will be transformed to achieve normality if needed. At this time, we will also assess the effectiveness of the randomization procedures. If between-group differences exist, relevant variables will be included as covariates in outcome analyses. We will also explore whether contamination is a significant issue by comparing members of the control groups reporting they were exposed to specific HOPE content to those who were not exposed to determine if such exposure impacts outcome, and control for exposure in analyses below if necessary. Although only a small percentage of participants in our pilot work reported initiation of a new medication (3.3%), change in dose or type of ongoing medications (3.3%), or cessation of a medication (5%), we will also explore whether medication changes during treatment impacted outcome, and control for medication changes in analyses if necessary (see below). Additionally, we will preliminarily investigate therapist effects on attendance, attrition, and primary outcomes and use this data to inform future research with HOPE that will more directly assess therapist effects. Finally, pattern mixture methods^{74, 75} will be used to assess the ignorability of missingness in all outcome analyses described below. All analyses will include an intent-to-treat analysis (using data from all randomized participants) and a minimal attendance analysis (i.e., attending at least $\frac{1}{2}$ of sessions). For intent-to-treat analyses, missing data will be handled using multiple imputation with an expectation maximization algorithm.

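### Therapists from two agencies are randomly assigned to HOPE or PCT with no stratification by agency described, so agency could coincide with treatment arm; blocking the draw on agency is a cheap improvement

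*Combined protocol and SAP*

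**What the plan says.** All references are to the combined protocol and SAP.

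- **C2, Therapists.** "Therapists for the intervention will consist of 4 community therapists", and "therapists will be recruited from the two local community mental health agencies". The number from each agency is not given.
- **C2, Therapist training procedures.** Therapists are nested in treatment: "We chose to train therapists in only one treatment modality". The allocation rule is one sentence: "Therapists will be randomly assigned to deliver either HOPE or PCT". The method, the number of therapists per arm and any stratification are not described. If adherence is poor, "the therapist will be replaced with another therapist who will have received the training"; the replacement's agency is not addressed.
- **C2, Randomization.** For participants the plan does name balancing factors: "We will stratify participants according to comorbid substance use disorder (SUD) and use of psychotropic medications". Neither therapist nor agency is among them.
- **C2, Sample and recruitment.** The plan allocates 93 women to each arm, which makes two therapists per arm the natural reading but does not state it.
- **C3, Data Analytic Plan.** "we will preliminarily investigate therapist effects on attendance, attrition, and primary outcomes". The stated use is to inform later research, and no agency term is named.

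**The concern.** With only four units to randomize, chance imbalance between arms is likely, and one form of it is severe: both HOPE therapists from one agency and both PCT therapists from the other. Arm and agency would then be the same variable, and no covariate adjustment could separate them, because neither agency would contribute to both arms.

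The rationale in C2 is that PCT controls for the nonspecific elements of therapy, so that a HOPE-PCT difference can be credited to what is specific to HOPE. Differences between agencies in clinical culture or prior training are nonspecific elements. In a confounded draw they would be read as treatment effect, in either direction.

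**Working it through.** **1. Chance of complete confounding.** The plan states no probability, so there is no figure to reproduce. The stated inputs are four therapists, two agencies and one treatment per therapist. The number per agency and the number per arm are unstated, so I enumerate the possibilities. A draw is completely confounded when the two arms share no agency.

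| Therapists per agency | Assignment rule | Completely confounded |
|---|---|---|
| 2 + 2 | exactly two per arm, C(4,2) = 6 draws | 2/6 = 1/3 |
| 2 + 2 | independent coin flips, 2^4 = 16 draws | 2/16 = 1/8 |
| 2 + 2 | coin flips, both arms staffed (14 draws) | 2/14 = 1/7 |
| 3 + 1 | exactly two per arm | 0/6 |
| 3 + 1 | independent coin flips | 2/16 = 1/8 (1/7 if both arms staffed) |
| 2 + 2 | randomized within agency, one to each arm | 0 |

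In the fourth row, one arm is always staffed by a single agency and the other is mixed, so the confounding is partial but occurs in all six draws.

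**2. Standard error implied by the plan.** The inputs, from C2, Adequacy of Sample Size, are effect size .60, effect-size variance .07 across 6 shelters, 25 women per shelter, .1 of variance explained by shelter and .3 by the baseline covariate.

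SE² = (.07 + 4 × .9 × .7 / 25) / 6 = (.07 + .1008) / 6 = .0285, so SE = .169.

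Check against the plan: the noncentrality is .60² / .0285 = 12.6 on (1, 5) df, which gives power .81 against the stated .80. Other ways of entering the shelter variance give .785 to .819. The standard error is therefore a fair reading of the plan.

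**3. Effect of a fully confounded draw.** Let ρ be the share of outcome variance due to agency. The documents give no value; I assume 1%, 2% and 5%. The difference between two agencies has variance 2ρ in standardized units, and in a confounded draw all of it is added to the treatment contrast. Treating the agency effect as normal, with a 5-df critical value of 2.571:

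type I error = 2 × P(t₅ > 2.571 / √(1 + 2ρ/.0285)).

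| ρ (assumed) | SD of bias, √(2ρ) | Reduced threshold | Type I error, confounded draw | Average over six 2:2 draws |
|---|---|---|---|---|
| .01 | .14 | 1.97 | .106 | .069 |
| .02 | .20 | 1.66 | .158 | .086 |
| .05 | .32 | 1.21 | .280 | .127 |

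The last column is 2/3 × .05 + 1/3 × the column before it. It assumes 2 + 2 therapists and similar caseloads, so that the agency difference cancels in the four mixed draws.

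**4. The 3 + 1 case with two per arm.** With equal caseloads, half the agency difference enters the contrast in every draw, adding variance 2ρ/4 = ρ/2. The SD of the bias is .07, .10 or .16, and type I error is .064, .078 or .120 for ρ = .01, .02 or .05.

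**The case against.** **The plan is silent, not explicit.** A reader might infer that assignment is unrestricted and that the chance of complete confounding is one in three. The text supports neither as fact. It gives no method, and the 1/3 needs both a 2 + 2 agency split and a fixed two per arm, which is itself a restriction. Over the unstated inputs the range is 0 to 1/3. This stands.

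**The larger error rates are conditional.** A reader might take .11, .16 and .28 as the trial's false-positive rates. They apply only if the confounded draw occurs, and only under variance shares that nothing in the documents supports or rules out. Over the random draw the agency difference has mean zero, and the averaged rates are lower. This also stands, though the trial makes one draw and must live with its result.

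**The plan limits differences between therapists.** All must be licensed at master's level, with at least two years of trauma experience and CBT training, and are screened by interview and role-play. Certification, two supervised training cases, weekly tape review, and group and individual supervision follow. Sessions take place in the shelter or another convenient place, and nothing locates them at the agencies. These measures make a large agency effect less plausible. They do not break the confounding if it arises.

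**Agency is the smaller part of the problem.** With two therapists per arm, individual differences remain confounded with treatment even after blocking. That is correct, and it limits what the fix achieves.

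**Replacements could mix the agencies.** It would therefore go too far to say that every woman in an arm must be seen by one agency's staff. But nothing in the plan requires a replacement to come from the other agency.

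**Conclusion.** The point holds in a limited form, as a cheap improvement. The plan describes nothing that would prevent agency from coinciding with treatment, and no analysis in C3 could separate the two if it did. The chance of complete coincidence is 1/3 with two therapists per agency and two per arm, 1/8 with coin flips (1/7 if both arms must be staffed), and 0 with 3 + 1 and two per arm, where the confounding is instead partial and certain.

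The consequence depends on an agency effect of unknown size. At assumed variance shares of 1% to 5%, type I error is about .11 to .28 in a fully confounded draw and about .07 to .13 averaged over the six 2:2 draws. The documents do not show that agencies differ, and the shared training and supervision may make the effect small. The case for change rests on how little it costs and on timing: it cannot be made once therapists have been assigned and trained.

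**What to change.** In C2, Therapist training procedures, state that the sponsor will aim to recruit two therapists from each agency and will randomize within agency, one to HOPE and one to PCT. Where feasible, draw a replacement from the same agency as the therapist replaced, for the same arm. Keep caseloads similar across therapists, since the agency difference cancels only to that extent. Report agency alongside the therapist-effects analysis in C3.

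Under 2 + 2 this takes the chance of complete confounding to zero. It needs no extra patients or data, only a restricted draw before training.

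There are two downsides. Needing two qualified therapists from each agency, and like-for-like replacements, is a mild recruitment constraint. Both treatments will also be present in each agency, so therapists should be told not to exchange materials. That contact is not new: four of the six 2:2 draws under 2 + 2 already produce it, and the plan puts all therapists in weekly group supervision together.

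The change removes the agency component only. Differences between individual therapists remain nested in arm and should be acknowledged as a limitation.

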
Assessment: Participants will be assessed at six primary time points: (1) baseline, (2) 1-week post-shelter (PS) treatment (tx), (3) 1-week PS, (4) 1-week post-tx (i.e., 13 weeks PS), (5) 6-months post-tx, and (6) 1-year post-tx using a combination of well-known structured interviews and self-report questionnaires with demonstrated reliability and validity. For data and safety monitoring purposes (see E2), participants will also complete an abbreviated assessment designed to assess for clinical deterioration and re-abuse at mid-shelter tx (i.e., 5 weeks after begin tx), mid-PS tx (i.e., 6-weeks PS) assessment, and 3- and 9-months post-tx (see Table 1). Assessment procedures will mirror those that have been successful in our pilot work with HOPE. While women are residents of the shelter, assessments will take place at the shelter. Follow-up assessments will occur at the safest and most convenient location for the women (e.g., hospital, public library, in-home visit). In the event that a participant cannot attend a follow-up assessment in person (e.g., moves out of state) interviews will be conducted via phone. Three blind research assistants will conduct all follow-up assessments, under the supervision of the project coordinator. The RAs will be trained in the administration of all interviews and research procedures. This training will include strategies for the accurate assessment of PTSD and IPV using training procedures already in place in [name] research lab. A minimum of 80% agreement on all ratings will be required to establish inter-rater reliability. The RAs will be blind to treatment condition, as well as to the study design and hypotheses. Table 1 contains a summary of measures given at each assessment period. All measures will be administered electronically with software available from Questionnaire Development System (QDS). Self-report measures will be administered with the Audio Computer Administered Self Interview (ACASI) module, and all interviews will be administered with the Computer Assisted Personal Interview (CAPI) module. We chose to use ACASI to increase women's likelihood of disclosing stigmatized experiences, to streamline data entry, and to improve data reliability.

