Primary outcomes include IPV-related PTSD severity and degree of re-abuse. PTSD symptom severity, as well as PTSD diagnostic status will be assessed with the **Clinician Administered PTSD Scale (CAPS⁵⁰)** at all major time points. PTSD will be assessed for both the index IPV and the other most traumatic event, allowing us to explore treatment effects both specific to IPV and more broadly. Self-report symptoms of PTSD severity will also be assessed with the **Davidson Trauma Scale (DTS⁵⁶)** at all time points. IPV severity will be assessed with the **Revised Conflict Tactic Scales (CTS2)** at all time-points. Abuse severity rather than

presence of abuse was chosen as a primary outcome as it is consistent with a large body of research demonstrating severity of a traumatic event, rather than the occurrence of the event itself to be an important predictor of PTSD severity⁵⁷. Further, given that the occurrence of abuse is not entirely in the victims' control, safety planning strategies seem more likely to assist women in reducing the overall severity of the abuse, rather than each individual act of abuse. We operationalized abuse severity as the sum of the number of abusive acts, a scoring method found to provide a valid measure of abuse severity⁵⁸.

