LIFE	X		X	X		X		X		X
CSQ						X		X		X

Note. MSSSI administered at any time point if participant endorses SI. CAPS administered at mid-tx assessments if DTS increases 50%. *Only the substance module of SCID-I/P administered at follow-up.

Adherence and Competence: All therapy sessions will be recorded. [name], a consultant on this project who is well-trained in treatment of IPV-related PTSD, as well as in HOPE, serving as a therapist in our pilot work with HOPE will rate adherence and competence of the delivery of 5% of randomly selected HOPE and PCT sessions (i.e., 74 HOPE and 74 PCT sessions). She will also participate in the PCT training with the study therapists and consult with [name] in order to develop competence in rating PCT sessions. HOPE and PCT have established adherence and competence scales used in prior research (see appendix)^{37, 46}.

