Mediators and Moderators of Treatment Response: Exploratory regression analyses will be conducted to evaluate whether treatment effects are mediated by degree of empowerment, effective use of resources, and trauma-related cognitions, as well s to determine if participants' PTSD symptoms post-treatment mediate severity of re-abuse over follow-up. The statistical significance of the mediated, or indirect effects, will be tested using bootstrapping methods which under most conditions, provide the most powerful way to obtain confidence intervals for mediated effects⁹⁰. Regression analyses will also be used to evaluate potential moderators of treatment response, that is, to determine for whom a relationship between intervention and treatment outcome exists. Interaction terms (i.e., treatment group X potential moderator) will be tested for minority status and for baseline measures of IPV severity, PTSD severity, attentional biases to trauma cues and physiological reactivity to trauma cues.

Treatment Integrity. Descriptive analyses will be run for the adherence and competence scales for both HOPE and PCT. Bivariate correlational analyses will be run to determine if degree of adherence and competence relates to outcome. Any cases where a session was found to have inadequate adherence and/or competence will not be used in analyses.

Figure 2.

	Year 1	Year 2	Year 3	Year 4
Start up	█			
Recruitment		█	█	
Intervention		█	█	
Follow up		█	█	█
Evaluation				█
Dissemination				█

D. Timeline and Milestones

Study time line for four-year project:

Start up period (Y1, Months 1-6): Includes program refinement, institutional review board approval, therapist, RA, project coordinator, rater, and assessment training, and database development. Recruitment period (Y 1 Mo 6- Y3 Mo 9). Intervention (Y1 Month 6 – Y3 Mo 12). Follow up (Y1 Month 9 Y 4 mo 11). Evaluation (Y5 mo 6-12): The data safety monitoring committee will meet bi-annually to evaluate the safety of the intervention program and to review blinded analysis and any adverse events. The analysis will begin after outcome assessments are complete and the data are cleaned. Dissemination (Y5 mo 6-12): Manuscript preparation, community and national presentations, focus groups with shelter and community staff and other stakeholders to assist in developing a dissemination plan to inform a future dissemination study of HOPE.

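### The 50% DTS rise that prompts a mid-treatment CAPS cannot occur from a reference score above two thirds of the DTS maximum

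*Combined protocol and SAP*

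**What the plan says.** Section C2 (Assessment) plans the CAPS "at all major time points. PTSD will be assessed for both the index IPV and the other most traumatic event". Table 1 matches this: the CAPS is marked at six visits and the DTS at all ten. The mid-shelter and mid-post-shelter treatment visits have a DTS and no CAPS. The note under Table 1 adds one on a condition: "CAPS administered at mid-tx assessments if DTS increases 50" percent.

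The purpose of the abbreviated visits is stated in C2 (Assessment): "For data and safety monitoring purposes (see E2), participants will also complete an abbreviated assessment designed to assess for clinical deterioration and re-abuse". The two that fall within treatment are timed as "mid-shelter tx (i.e., 5 weeks after begin tx), mid-PS tx (i.e., 6-weeks PS) assessment". The next scheduled CAPS after the second of them is at "1-week post-tx (i.e., 13 weeks PS", that is, post-shelter week 13.

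C2 (Clinical Deterioration/Suicidal Risk) says that women are taken out of the treatment phase for "clinical deterioration or suicidal risk (see E1 for procedures, assessment & definitions". Sections E1 and E2 are not in the text available for this review.

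**The concern.** The note converts a self-reported worsening into a clinician-rated PTSD assessment. It does so by a percentage rise, and the room for a percentage rise shrinks as the reference score grows. Above some point on the scale the condition cannot be met however much a woman worsens. The rule then works least well for the women with the most severe scores, at visits designed to detect deterioration.

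High scores are plausible here. Every participant has IPV-related PTSD on the CAPS at entry (C2, Sample and recruitment), and the pilot population had symptoms lasting nearly 38 months on average (C1). What is at stake is a timely CAPS for a woman who worsens from a high score. If the mid-post-shelter visit does not prompt one, the next scheduled CAPS is 13 − 6 = 7 weeks later. From the mid-shelter visit the wait depends on length of shelter stay, and the documents do not fix it.

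**Working it through.** **Inputs.** The 50% trigger (Table 1 note); the visit schedule (Table 1 and C2, Assessment); 186 women (C2, Study Design). The DTS maximum is not given. Call it M; the result does not depend on its value. The 50% is a chosen threshold, so there is no plan figure to reproduce.

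**Step 1: when the trigger can be reached.** From a reference score R, a 50% rise requires a score of 1.5R. This is attainable only if 1.5R ≤ M, that is R ≤ M/1.5 = 0.667M. The largest possible relative rise is M/R − 1. The share of the remaining room that must be used is 0.5R/(M − R).

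| R | Rise needed now | Share of remaining room | Largest possible rise | Reachable? |
|---|---|---|---|---|
| 0.40M | 0.20M | 33% | 150% | yes |
| 0.50M | 0.25M | 50% | 100% | yes |
| 0.60M | 0.30M | 75% | 66.7% | yes |
| 0.667M | 0.333M | 100% | 50% | only at the maximum |
| 0.70M | 0.35M | 117% | 42.9% | no |
| 0.80M | 0.40M | 200% | 25% | no |
| 0.90M | 0.45M | 450% | 11.1% | no |

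If the 50% were read as half of the scale range (assuming the scale starts at 0), the cutoff would fall to 0.50M and the gap would be wider.

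**Step 2: which score is R.** At mid-shelter the only earlier scheduled DTS is baseline, so R is the baseline score. At mid-post-shelter there are several earlier scores, and the note does not choose among them. The choice matters. Take a woman at 0.80M at baseline, 0.40M at 1 week post-shelter and 0.70M at mid-post-shelter. Measured from baseline she has fallen. Measured from the previous visit she has risen 0.30/0.40 = 75%, which triggers a CAPS.

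**Step 3: how many women.** The documents give no DTS mean, SD or range, so this cannot be computed. Each 10% of the sample is 0.10 × 186 = 18.6, about 19 women. Purely as an assumption, a normal reference score with mean 40% to 70% of M and SD 15% to 20% of M puts about 4% to 59% of women above the cutoff. That range is too wide to serve as an estimate.

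**Step 4: an alternative that can be reached.** Let the trigger be a rise of 0.5R or of 0.5(M − R), whichever is smaller. For R ≤ 0.50M, 0.5R is the smaller, so nothing changes. Above 0.50M the rise needed is 0.5(M − R): 0.20M from 0.60M, 0.15M from 0.70M, 0.10M from 0.80M and 0.05M from 0.90M. This is always less than the room left, so it is reachable from every R below M. From M itself no rise is possible under any rule.

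**The case against.** The strongest reply is that the operative rule may lie elsewhere. The note is a footnote to a summary table and does not say that its trigger is the only one; that reading comes from the empty CAPS cells. Deterioration is defined in E1 and the interim visits are governed by E2, and either may contain an absolute criterion. This stands, and the absence of those sections here is not a gap in the plan. It confines the point to the note but does not make the note's trigger reachable.

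Monitoring also continues without the extra CAPS. The DTS and CTS-2 are collected at all ten visits, so worsening is recorded. The suicidality scale is given whenever ideation is endorsed. Supervisors review therapists' "audiotapes on a weekly basis and provide feedback during individual and group supervision sessions". Section D adds that "The data safety monitoring committee will meet bi-annually to evaluate the safety of the intervention program". All of this is right and keeps the severity low, although none of it by itself gives a CAPS to a woman whose DTS worsens from a high reference.

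A reader might infer that women who start highest are shut out at both visits. The documents support this only at mid-shelter. At mid-post-shelter it depends on the unstated reference, and the woman in Step 2 would trigger under the previous-visit reading. A reader might also infer that such women cannot be withdrawn for deterioration. No available text makes a CAPS a condition for removal.

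**Conclusion.** The point holds as a minor safety issue confined to the Table 1 note. The ceiling is exact for a relative rise on any bounded scale: above two thirds of the DTS maximum the stated trigger cannot fire. This is certain for high baseline scores at mid-shelter. At mid-post-shelter it holds for whichever reference score is used.

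The number of women affected is unknown. The conclusion assumes that the 50% is a relative rise in the raw score and that E1 and E2 do not already supply another route to a CAPS. It would be wrong to read this as a threat to the efficacy result: the note concerns only additional CAPS interviews at safety visits, and the between-arm analysis and the sample size are unaffected.

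**What to change.** Keep the 50% trigger, state the reference, and add an alternative that can be reached. For example: *Give the CAPS at a mid-treatment assessment when DTS has risen, relative to baseline or to the previous assessment, by 50% or by at least half of the distance left to the DTS maximum.* Align the wording with E1 and E2. If either already holds an absolute rule, a cross-reference in the note is enough.

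Allowing either reference matters. Fixing it at baseline alone would remove the relapse trigger for the woman in Step 2, if the previous visit is what the note intends. Every condition requires a rise, so a woman whose score is no higher than either reference never triggers a CAPS.

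The cost is one line plus some extra interviews at visits already scheduled. For each 10% of women who newly qualify at both visits this is 18.6 × 2 = 37.2, about 37 interviews, or 3.3% of the 186 × 6 = 1,116 scheduled CAPS. The true share is unknown, and women who leave shelter before week 5 of treatment may not have the mid-shelter visit. There are two trade-offs. The threshold also falls for reference scores between one half and two thirds of the maximum (0.30M to 0.20M at 0.60M). Near the ceiling, small rises that may be noise will prompt a few interviews.
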